### **5.1.4 Pregnancy**

If a participant inadvertently becomes pregnant while on treatment with pembrolizumab, the participant will be immediately discontinued from study intervention(s). The site will contact the participant at least monthly and document the participant's status until the pregnancy has been completed or terminated. The outcome of the pregnancy will be reported to Merck within 2 working days if the outcome is a serious adverse experience (e.g. death, abortion, congenital anomaly, or other disabling or life-threatening complication to the mother or newborn). The study Investigator will make every effort to obtain permission to follow the outcome of the pregnancy and report the condition of the fetus or newborn to Merck. If a male participant impregnates his female partner, the study personnel at the site must be informed immediately and the pregnancy must be reported to Merck and followed as described in Section 6.2.

## **5.2 Trial Intervention(s)**

The intervention(s) to be used in this trial is outlined below in **Table 5**

Table 5 Trial Intervention(s) Drug	Dose/Potency	Dose Frequency	Route of Administration	Regimen/Treatment Period	Use
Mitotane	1000-6000 mg	Daily	PO	4 weeks lead-in phase* (+/-5 days) followed by maintenance therapy per acceptable clinical standards	Standard of Care
Pembrolizumab	400 mg	Q6W	IV infusion	Day 1 of each 6-week cycle (after MT lead-in phase)	Experimental

\* The lead-in phase is primarily designed to ensure patients safety and to have initial evaluation of potential AEs attributed to MT use with particular attention to liver enzymes. If MT use caused elevated ALT or AST during the lead-in phase not meeting eligibility criteria for LFTs or if participants developed  $\geq$  G3 non-hematological toxicity, then these patients will not go through the combination therapy and may come off protocol at the discretion of the PI and will be replaced if excluded by other patients and considered as screen failure. Patients who were on prior MT therapy must complete 28 days of MT use prior to moving to combination therapy and must meet eligibility criteria stated at screening phase and will not need to have the lead-in phase assessment.

Trial intervention(s) should begin as close as possible to the date on which intervention is allocated/assigned.

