### **3.0 OBJECTIVE(S), HYPOTHESIS(ES), AND ENDPOINT(S)**

#### **3.1 Primary Objective(s), Hypothesis(es), and Endpoint(s)**

(1) **Objective:** Assess the clinical efficacy of the combined use of MT with PEM in patients with advanced ACC.

**Hypothesis:** We hypothesize that adding PEM will enhance the clinical efficacy of MT. This additive/synergistic effect could be related to the intrinsic adrenolytic activity of MT that could lead to antigens exposures to immune cells. Furthermore, the cortisol lowering effect of mitotane is expected to alter the tumor microenvironment leading to a change the milieu of the tumor infiltrating immune cells to make ACC more susceptible to PEM. Also, cortisol lowering can reduce lymphocytes inhibition and enhances the efficacy of PEM.

**Primary Endpoint:** Overall response rate (ORR) assessed objectively using RECIST 1.1 criteria defined as the percentage of patients who have a partial or complete response to the combined treatment of MT plus PEM

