## **5.7 Participant withdrawal From Study**

A participant must be withdrawn from the study if the participant or the participant's legally acceptable representative withdraws consent from the study.

If a participant withdraws from the study, they will no longer receive study intervention or be followed at scheduled protocol visits.

Specified details regarding procedures to be performed at the time of withdrawal from the study are outlined in Section 6.1.6.1.

**5.8 Participant Replacement Strategy:** Patients who cannot join the combination of the study and deem ineligible to move from the lead-in phase to the combination therapy phase of the study will be replaced by other participants.

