### **6.2 Adverse Events (AEs), Serious Adverse Events (SAEs), and Other Reportable Safety Events**

The definitions of an AE or SAE, as well as the method of recording, evaluating, and assessing causality of AE and SAE and the procedures for completing and transmitting AE, SAE, and other reportable safety event reports can be found in Appendix 5.

Adverse events, SAEs, and other reportable safety events will be reported by the participant (or, when appropriate, by a caregiver, surrogate, or the participant's legally authorized representative).

The investigator and any designees are responsible for detecting, documenting, and reporting events that meet the definition of an AE or SAE as well as other reportable safety events. Investigators remain responsible for following up AEs, SAEs, and other reportable safety events for outcome.

The investigator, who is a qualified physician, will assess events that meet the definition of an AE or SAE as well as other reportable safety events with respect to seriousness, intensity/toxicity and causality. **Time Period and Frequency for Collecting AE, SAE, and Other Reportable Safety Event Information**

All AEs, SAEs, and other reportable safety events that occur after the consent form is signed but before intervention allocation/randomization must be reported by the investigator if the participant is receiving placebo run-in or other run-in treatment, if the event causes the participant to be excluded from the study, or is the result of a protocol-specified intervention, including but not limited to washout or discontinuation of usual therapy, diet, or a procedure.

- All AEs from the time of intervention allocation/randomization through 30 days following cessation of study intervention must be reported by the investigator.

- All AEs meeting serious criteria, from the time of intervention allocation/randomization through 90 days following cessation of study intervention or 30 days following cessation of study intervention if the participant initiates new anticancer therapy, whichever is earlier, must be reported by the investigator.

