**Table 9 Reporting Time Periods and Time Frames for Adverse Events and Other Reportable Safety Events**

Type of Event	Reporting Time Period: Consent to Randomization/Allocation	Reporting Time Period: Randomization/Allocation through Protocol-specified Follow-up Period	Reporting Time Period: After the Protocol-specified Follow-up Period	Time Frame to Report Event and Follow-up Information to Merck:
Serious Adverse Event (SAE) including Cancer and Overdose	Report if: - due to protocol-specified intervention - causes exclusion - participant is receiving placebo run-in or other run-in treatment	Report all	Report if: - drug/vaccine related. (Follow ongoing to outcome)	Within 2 business days but no longer than 3 calendar days of receipt of information
Pregnancy/Lactation Exposure	Report if:  - participant has been exposed to any protocol-specified intervention (eg, procedure, washout or run-in treatment including placebo run-in)  Exception: A positive pregnancy test at the time of initial screening is not a reportable event.	Report all	Previously reported – Follow to completion/termination; report outcome	Within 2 business days but no longer than 3 calendar days of receipt of information
Event of Clinical Interest (require regulatory reporting)	Report if: - due to intervention - causes exclusion	Report - potential drug-induced liver injury (DILI) - require regulatory reporting	Not required	Within 2 business days but no longer than 3 calendar days of receipt of information

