## 7.0 STATISTICAL ANALYSIS PLAN

We will simultaneously monitor efficacy and toxicity using the Bayesian optimal phase 2 (BOP2) design (Zhou, Lee and Yuan, 2017). Specifically, let  $n$  denote the interim sample size, and  $N$  denote the maximum sample size. Let  $Y_{eff}$  and  $Y_{tox}$  denote the binary efficacy and toxicity endpoints, with  $Y_{eff} = 1$  and  $Y_{tox} = 1$  indicating that patients experience efficacy and toxicity, respectively. We assume that the joint distribution of  $(Y_{eff}, Y_{tox})$  follows a multinomial distribution with four elementary outcomes:  $(Y_{eff}, Y_{tox}) = (1, 1), (1, 0), (0, 1)$  and  $(0, 0)$ . Let  $\mathbf{p} = (P_{11}, P_{10}, P_{01}, P_{00})$  denote the probabilities of observing the four outcomes, and let  $p_{eff} = Pr(Y_{eff} = 1)$ ,  $p_{tox} = Pr(Y_{tox} = 1)$  and  $p_{eff,tox} = Pr(Y_{eff} = 1, Y_{tox} = 1)$ . When efficacy and toxicity endpoints are monitored separately, the joint distribution reduced to marginal distribution of efficacy and marginal distribution of toxicity, respectively. For trial monitoring and decisions, extreme toxicities (TOX) will be defined as any grade 3 or higher adverse event that is possibly, probably, or related to therapy received on this protocol. Any grade 3 or higher adverse event that is potentially treatable with steroids or hormonal replacement will only count as an extreme toxicity if it does not improve to grade 1 or better within 2 weeks of therapy.

The treatment is deemed unacceptable if  $p_{eff} \leq 0.23$  or  $p_{tox} > 0.5$ . Thus, we will stop enrolling patients and claim that the treatment is unacceptable if

$$Pr(p_{eff} > 0.23 | data) < \lambda \left( \frac{n}{N} \right)^\alpha,$$

or

$$Pr(p_{tox} \leq 0.5 | data) < \lambda \left( \frac{n}{N} \right)^{\alpha/3},$$

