where  $\lambda=0.5$  and  $\alpha=1$  are design parameters optimized to maximize the study power, i.e., probability of correctly concluding an efficacious and safe treatment as acceptable when  $p_{eff} = 0.3$ ,  $p_{tox} = 0.3$  and  $p_{efftox} = 0.18$ , while controlling that the probability of incorrectly claiming an inefficacious and toxic treatment, i.e., type I error, with  $p_{eff} = 0.23$ ,  $p_{tox} = 0.5$  and  $p_{efftox} = 0.15$ , to 9.5%. Note that in the safety stopping rule, the original publication of the design used the probability cutoff  $\lambda(n/N)^\alpha$ , here the attenuation factor 3 is added (i.e.,  $\alpha/3$ ) to obtain stricter interim stopping boundaries to enhance safety.

For the purposes of interim monitoring, toxicities and responses will be monitored for 24 weeks post start of the combination therapy.

This optimization is performed assuming a vague Dirichlet prior  $Dir(0.15, 0.08, 0.35, 0.42)$  for  $\mathbf{p}$ . The prior is chosen such that it corresponds to a prior effective sample size of 1 patient, and the prior estimates of  $p_{eff}$  and  $p_{tox}$  match the values specified when the treatment is unacceptable. The above decision rule leads to the following optimal stopping boundaries:

*Table 1: Optimized stopping boundaries*

# patients treated	Stop if # response <=	OR # toxicity	
		<=	>=
10	0	6	
20	3	11	
35	7	18	
50	11	25	

When the total number of patients reaches the maximum sample size of 50, we conclude that the treatment is acceptable if the number of responses are greater than 11, and the number of toxicities are less than 25; otherwise we conclude that the treatment is unacceptable. The go/no-go criteria in Table 1 are non-binding.

Below are the operating characteristics of the design based on 10000 simulations using the BOP2 web application (BOP2 V1.4.7.0), which is available at <http://www.trialdesign.org>.

*Table 2: Operating characteristics*

Scenario	Pr(Eff)	Pr(Tox)	Pr(Eff & Tox)	Early Stopping (%)	Claim Acceptable (%)	Average Sample Size
1	0.23	0.5	0.15	83.15	9.47	23.0
2	0.30	0.3	0.18	24.46	71.38	42.9

ORR will be summarized with a 95% confidence interval (Clopper-Pearson exact method).

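### Patients who take protocol mitotane and fail the lead-in for toxicity are coded as screen failures and replaced; the plan neither secures their adverse events in the safety results nor gives an all-starter response rate.

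*Combined protocol and SAP*

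**What the plan says.** - **Lead-in mitotane is trial treatment.** Table 5 (Section 5.2) lists it as a trial intervention, lasting 4 weeks (+/-5 days). Patients already on mitotane skip the lead-in once they have completed 28 days of the drug.
- **Lead-in failures.** A patient whose ALT or AST no longer meets the eligibility limit, or who has grade 3 or higher non-hematological toxicity, does not go on to the combination and "may come off protocol at the discretion of the PI". Those excluded "will be replaced if excluded by other patients and considered as screen failure". The same footnote appears under Table 1 in Section 2.2. Section 5.8 adds that patients ineligible to move to the combination "will be replaced by other participants".
- **Efficacy.** Section 3.1 defines ORR as the "percentage of patients who have a partial or complete response to the combined treatment of MT plus PEM". Section 3.2 counts OS and PFS from combination therapy.
- **Toxicity monitoring.** Section 7.0 defines the monitored toxicity (TOX) as "any grade 3 or higher adverse event that is possibly, probably, or related to therapy received on this protocol", with an exception for events that respond to steroids or hormone replacement. It then says that "toxicities and responses will be monitored for 24 weeks post start of the combination therapy".
- **Adverse-event reporting.** Under Section 6.2, events between consent and allocation "must be reported by the investigator if the participant is receiving placebo run-in or other run-in treatment", or if they cause exclusion. Table 9 has the same trigger for SAEs: "participant is receiving placebo run-in or other run-in treatment".
- **Adverse-event tables.** Section 7.0 plans frequency tables and the highest grade per subject. It defines no safety analysis set. In Table 1 the adverse-event row has no mark in the lead-in column.

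**The concern.** A screen failure is normally someone who was never treated. These patients have consented, met the eligibility criteria and taken a drug listed as trial intervention, and they are stopped because of what happened on it. The label puts treated patients in a category that analysis datasets usually leave out, and replacement fills their places with people who tolerated mitotane.

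Two things are at stake. The first is safety: Section 3.2 has a hypothesis about the adverse-event profile of mitotane, and patients who cannot get past the first month because of mitotane toxicity are among the most informative on it. The second is interpretation: for a mitotane-naïve patient the strategy begins with mitotane, and a response rate among those who reached pembrolizumab does not tell a clinician what to expect from the day treatment starts.

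**Working it through.** **1. The plan's own figures.** The Section 7.0 rule has looks at 10, 20, 35 and 50 patients; it stops at responses ≤ 0/3/7/11 or toxicities ≥ 6/11/18/25. The marginal priors implied by the Dirichlet are Beta(0.23, 0.77) for response and Beta(0.5, 0.5) for toxicity. With cutoffs 0.5(n/50) and 0.5(n/50)^(1/3), the boundaries come out exactly as printed. An exact recursion over the four-outcome multinomial gives:

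| Scenario | Acceptable, stated | Acceptable, exact |
|---|---|---|
| ORR 0.23, TOX 0.50, both 0.15 | 9.47% | 9.56% |
| ORR 0.30, TOX 0.30, both 0.18 | 71.38% | 71.91% |

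The differences fit the error of 10000 simulations (about 0.3 and 0.45 points). The design figures are sound for the patients they describe, namely those who start the combination.

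**2. Where a lead-in failure is counted.**

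| Result | Counted? | Basis |
|---|---|---|
| ORR denominator | No | Section 3.1: response to the combination; place refilled under Section 5.8 |
| OS and PFS | No | Section 3.2: time origin is combination therapy |
| TOX monitoring | Unclear from the definition, no from the window | Section 7.0: protocol therapy includes lead-in mitotane, but the 24 weeks begin with the combination |
| AE/SAE reporting | Yes | Section 6.2 and Table 9 |
| AE tables | Not stated | Section 7.0: no safety set; Table 1: no lead-in mark; label says screen failure |

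**3. Size.** Inputs: maximum N = 50; the least favourable passing results are 12 responses (more than 11 needed) and 24 toxicities (fewer than 25 needed). The documents give neither the lead-in loss f nor the share s of the 50 combination patients who had a lead-in. Assume f = 10%, with s = 1, 0.5 or 0.25.

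Starters S = 50(1 − s) + 50s/(1 − f); lost L = S − 50. All-starter ORR = 12/S. Toxicity ceiling = (24 + L)/S, which counts every loss as a TOX.

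| s | S | L | ORR among starters | Toxicity, at most |
|---|---|---|---|---|
| 1 | 55.56 | 5.56 | 12/55.56 = 21.6% | 29.56/55.56 = 53.2% |
| 0.5 | 25 + 27.78 = 52.78 | 2.78 | 12/52.78 = 22.7% | 26.78/52.78 = 50.7% |
| 0.25 | 37.5 + 13.89 = 51.39 | 1.39 | 12/51.39 = 23.35%, about 23.4% | 25.39/51.39 = 49.4% |

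In whole patients, 12/52 = 23.1% and 12/53 = 22.6%, so three lead-in failures take a just-passing ORR below 23%. If all patients have a lead-in, the break-even is 12/0.23 = 52.2 starters, a loss of 1 − 50/52.2 = 4.2%.

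Away from the boundary, 15/50 (30.0%, 95% CI 17.9 to 44.6) with six lead-in failures becomes 15/56 (26.8%, 15.8 to 40.3).

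**4. Why the toxicity column is a ceiling.** The ALT/AST trigger is the Table 4 limit: 2.5 × ULN, or 5 × ULN with liver metastases. Grade 3 in Table 6 starts above 5 × ULN with a normal baseline. A patient can fail the lead-in without a grade 3 event. TOX also requires relatedness and carries the steroid/hormone exception.

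**The case against.** The strongest defence has four parts.

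- **The endpoint is response to the combination.** A patient who never receives pembrolizumab cannot meet it, and for lead-in patients the response baseline is the scan around Cycle 1 Day 1. This stands. The primary ORR is correct under its own definition, and the all-starter figure is a supplement.
- **The events are not lost.** A reader might infer from the screen-failure label that grade 3 or higher lead-in events disappear from the reported results. The documents do not say so. Section 6.2 requires run-in events, and events that cause exclusion, to be reported, and the adverse-event summary in Section 7.0 names no exclusion. This stands as far as reporting goes. Reporting by the investigator does not settle who is in the table, and on that the plan is silent.
- **Removal is conditional and partial.** Coming off protocol is at the investigator's discretion, the screen-failure label applies to those excluded, and patients already on mitotane have no lead-in. This stands, and it is why the illustration varies the lead-in share.
- **The go/no-go limits are set for combination-treated patients.** A reader might infer that replacement inflates the design's false-positive rate. If the null (ORR 0.23, TOX 0.50) is imposed on all starters, everyone has a lead-in and loss is 10%, acceptance rises from 9.6% to 26.6% when every loss is a TOX, or to 13.8% when half are. But the plan does not set its null on all starters, so these figures describe a different question and do not show that the stated error rate is wrong.

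**Conclusion.** The point holds as a gap in analysis sets and labelling. Patients treated with protocol mitotane and stopped for toxicity are, if excluded, coded as screen failures and replaced. They are outside the ORR, OS and PFS sets and the toxicity monitoring window. Their adverse events must be reported, but the plan does not ensure that they reach the safety tables. The TOX definition and the monitoring window in Section 7.0 also disagree on whether lead-in events count.

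The effect is modest and rests on assumptions. At 10% lead-in loss and a just-passing result, ORR falls from 24.0% by 0.6 to 2.4 points and the toxicity rate rises from 48% by at most 1.4 to 5.2 points, according to whether a quarter or all of the patients have a lead-in. The documents support neither the reading that safety events are deliberately dropped nor the reading that the primary analysis is invalid.

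**What to change.** Keep the combination-treated primary set and the go/no-go rule. Then:

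1. Code these patients as lead-in discontinuations, with the reason, in place of screen failures (Table 1 and Table 5 footnotes; align Section 5.8).
2. In Section 7.0, define the adverse-event population as everyone who took protocol mitotane or pembrolizumab, and show lead-in events separately. Mark the lead-in cell of the adverse-event row in Table 1.
3. State in Section 7.0 whether lead-in events count as TOX, so that the definition and the 24-week window agree.
4. Report the number of patients who entered the lead-in, the number who failed it and why, and an all-starter ORR (no combination counted as non-response) as a supportive result beside the primary ORR.

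The cost is a little more analysis on events that are already reportable, and a second, slightly lower ORR to explain. Sample size, stopping boundaries and clinical procedures do not change.

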### 5.2.1 Treatment

- Pembrolizumab will be given for a maximum of 2 years i.e. a total of 18 cycles of pembrolizumab with the Q6 week dosing.
- Mitotane will be given following standards of clinical practice and could extend beyond the study period

### 5.2.2 Second Course

N/A

### 5.2.3 Timing of Dose Administration

Trial interventions should be administered on Day 1 of each cycle after all procedures/assessments have been completed as detailed on the Schedule of Activities, Section 2.2. Trial interventions may be administered up to 5 days before or after the scheduled Day 1 of each cycle due to administrative reasons.

All trial interventions will be administered on an outpatient basis.

Pembrolizumab 400 mg will be administered as a 30-minute IV infusion every 6 weeks. Sites should make every effort to target infusion timing to be as close to 30 minutes as possible. However, given

the variability of infusion pumps from site to site, a window of -5 minutes and +10 minutes is permitted (i.e., infusion time is 30 minutes: -5 min/+10 min).

MT use will follow acceptable clinical practice pattern with starting dose of 500 mg PO BID or TID to be titrated every to achieve therapeutic serum level of 14-20 mg/L (maximum dose 6,000 milligrams per day). For MT naïve patients, the first 4 weeks (+/- 5 days) will be a lead-in phase then they will continue MT therapy in combination with PEM in 6-week cycles.

#### **5.2.4 Dose Modification and toxicity management for immune-related AEs associated with pembrolizumab and IO combination partners**

AEs associated with pembrolizumab or IO/IO combination exposure, may represent an immunologic etiology. These immune-related AEs (irAEs) may occur shortly after the first dose or several months after the last dose of pembrolizumab/combination treatment and may affect more than one body system simultaneously. Therefore, early recognition and initiation of treatment is critical to reduce complications. Based on existing clinical study data, most irAEs were reversible and could be managed with interruptions of pembrolizumab/combination treatment, administration of corticosteroids and/or other supportive care. For suspected irAEs, ensure adequate evaluation to confirm etiology or exclude other causes. Additional procedures or tests such as bronchoscopy, endoscopy, skin biopsy may be included as part of the evaluation. Dose modification and toxicity management guidelines for irAEs associated with pembrolizumab/combination treatment are provided in Table 6.

#### **Attribution of Immune-Related Toxicity:**

When study interventions are administered in combination, attribution of an adverse event to a single component is likely to be difficult. Therefore, while the investigator may attribute a toxicity event to the combination, to pembrolizumab, or to MT, all IO drugs must be held according to the criteria in [Table 6 Dose Modification and Toxicity Management Guidelines for Immune-Related Adverse Events Associated with Pembrolizumab].

